6. MILESTONES

Milestone	Planned date
Start of data collection	31 August 2021
Registration in the EU PAS register	08 June 2021
Progress report	01 September 2021
Interim Reports	01 March 2022 01 September 2022 01 March 2023 01 September 2023 01 March 2024
End of data collection	31 October 2023
Final study report	30 September 2024

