The study population of Pfizer-BioNTech COVID-19 mRNA vaccine recipients will be described in terms of demographic and health history characteristics, along with vaccination characteristics such as number of doses received and interval between doses. The incidence rates of medically attended safety events of interest will be estimated in the primary safety dataset of participants who enroll within 2 days of vaccination. Rates will also be estimated for the overall study population and within subcohorts of interest such as pregnant vaccine recipients, immunocompromised participants, and within age-categories. The final analysis will also be conducted for the following additional subcohorts of interest: Pfizer-BioNTech vaccine only; Heterologous vaccination (Pfizer-BioNTech booster[s] only; Heterologous primary course; Other combination heterologous vaccine course/booster). For events with a

sufficient number of cases, the observed rate will be compared with expected rates where available from historical or concurrent rates as reported in the scientific literature or other sources including those reported by the EMA-funded COVID-19 vaccine monitoring ACCESS program. For selected endpoints, such as those with acute onset and a definable risk window, a SCRI analysis will be implemented if case counts are sufficient. All statistical analyses will be described in a statistical analysis plan (SAP).

Milestones:

Data collection is planned to start 31 August 2021. Twice yearly interim reports are planned until 01 March 2024, with the final study report planned for 30 September 2024.

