9. RESEARCH METHODS

9.1. Study design

This is a prospective, observational, multi-center, non-interventional PASS conducted to evaluate safety of study participants receiving the Pfizer-BioNTech COVID-19 mRNA vaccine using a combination of primary data collection and secondary data analysis. This study will not provide or make recommendations on any vaccine use. Participants will be invited to enroll and consented in the study after the decision has been made to administer the vaccine, and participation in this study will not change or influence a participant's standard of care in any way. There are no protocol-mandated visits or procedures associated with the study. The study period is 30 months. Each participant will be followed from baseline (vaccination dose received at index date, where index date is defined as the date of Pfizer-BioNTech COVID-19 mRNA vaccine dose received within the 5 days prior to enrolment, regardless of dose number) until death, withdrawal of consent, loss to follow-up, 24 months or end of study period, whichever occurs first.

Data will be collected at baseline directly from the participants receiving the vaccine and/or their designee; this may include a health care provider (HCP) or study staff at the site administering the vaccine. Follow-up data on medically attended safety events of interest will be collected directly from persons receiving the vaccine.

[figure not shown]
This study will collect information on all reported occurrences of the medically attended safety events of interest, which is based on the AESI lists specified by ACCESSS and SPEAC/Brighton Collaboration, for which the participant sought medical care during the study period. Participants will choose their preferred method for submitting follow-up data:

- Completing questionnaires via a participant portal within the study website or mobile app, or
- Telephone interview via outbound calls from the IQVIA call center.

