9.2. Setting

This primary data collection study will aim for up to 10,000 vaccine recipients with 2 years of follow-up data. In order to reach this estimated sample size of vaccine recipients with complete data, 13,334 participants will be targeted for enrolment, assuming a 25% dropout rate over the 2-year follow-up period. The study will be conducted in Germany, Italy and Spain in a total of approximately 20 centers. Other countries may be included in addition to, or as a replacement, for one or more of these countries, as required to fulfill study objectives.

It is anticipated that participants will be enrolled from settings based upon the regional availability and distribution of vaccine according to national or regional COVID-19 preparedness plans and may include physician offices, hospitals, pharmacies, and/or vaccination centers. Site selection criteria will include the projected availability of eligible participants in the enrolment period and the availability of physician (and other site staff) time to complete brief baseline case report forms (CRFs) where required. Selection criteria and basic site information (e.g. site size, site type) will be collected via a site qualification survey.

Limited inclusion/exclusion criteria will be applied in this study, to ensure comprehensive capture of individuals receiving the Pfizer-BioNTech COVID-19 mRNA vaccine in real-world settings.

Participants will be considered enrolled if they meet the inclusion/exclusion criteria below, have provided informed consent (as required per local regulations), and have reported the date of Pfizer-BioNTech COVID-19 mRNA vaccination at baseline.

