9.2.1. Inclusion criteria

Participants must meet all of the following inclusion criteria to be eligible for inclusion in the study:

1. Participant's age is 18 years and above, and in accordance with the approved product label of the country where the study is conducted.
2. Enrolment within 5 days of receipt of any dose (i.e. first, second, or any subsequent booster dose) of the Pfizer-BioNTech COVID-19 mRNA vaccine.

Note:

Heterologous primary vaccination (two different COVID-19 vaccines [different manufacturers] received for the first and second doses of a primary [initial] course) and heterologous boosting (a third dose of a different manufacturers COVID-19 vaccine as a booster 3 to 6 months after a primary vaccination course) are now commonplace.

Individuals receiving heterologous booster doses are allowed to enroll in this study, if the booster dose received is the Pfizer-BioNTech COVID-19 mRNA vaccine. However, if a participant is enrolling at second Pfizer-BioNTech COVID-19 mRNA vaccine dose, the first dose received must have also been the Pfizer-BioNTech COVID-19 mRNA vaccine². If a participant is enrolling at second or booster dose of Pfizer-BioNTech COVID-19 mRNA vaccine, the participant must be able to provide the date and manufacturer of all previous COVID-19 vaccine doses received in order to be eligible for inclusion.

3. Adult participants willing to provide informed consent according to local regulations and complete all study procedures in accordance with the protocol, including consent for the study team to contact the treating HCP or healthcare facility to obtain additional information related to safety events reported by the participant.

² Including patients receiving the Pfizer-BioNTech COVID-19 mRNA vaccine as their second dose, who have not received the Pfizer-BioNTech COVID-19 mRNA vaccine as their first dose, would result in any vaccine effects being difficult to distinguish between manufacturers. No such restrictions are placed upon participants enrolling at booster doses, as the time window between doses is anticipated to be longer, with reduced likelihood of overlapping risk intervals.

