1.1 Does the protocol specify timelines for				
1.1.1 Start of data collection ⁴				6
1.1.2 End of data collection ⁵				6
1.1.3 Progress report(s)				6
1.1.4 Interim report(s)				6
1.1.5 Registration in the EU PAS Register®				6
1.1.6 Final report of study results.				6

Comments:

Section 2: Research question	Yes	No	N/A	Section Number
2.1 Does the formulation of the research question and objectives clearly explain:				
2.1.1 Why the study is conducted? (e.g. to address an important public health concern, a risk identified in the risk management plan, an emerging safety issue)				7
2.1.2 The objective(s) of the study?				8

⁴ Date from which information on the first study is first recorded in the study dataset or, in the case of secondary use of data, the date from which data extraction starts.

⁵ Date from which the analytical dataset is completely available.

Section 2: Research question	Yes	No	N/A	Section Number
2.1.3 The target population? (i.e. population or subgroup to whom the study results are intended to be generalised)				9.2
2.1.4 Which hypothesis(-es) is (are) to be tested?				
2.1.5 If applicable, that there is no a priori hypothesis?				

Comments:

Section 3: Study design	Yes	No	N/A	Section Number
3.1 Is the study design described? (e.g. cohort, case-control, cross-sectional, other design)				9.1

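### Section 6 ends data collection after 26 months, against a stated 30-month study; on that end date the plan of 13,334 enrolled at 25% dropout cannot yield 10,000 participants with 2 years of data

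*Protocol*

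**What the plan says.** - **Start.** Section 6 and the abstract agree: "Data collection is planned to start 31 August 2021".
- **End.** Section 6 puts the end of data collection at "31 October 2023". A footnote in the ENCePP checklist (Annex 2) defines that milestone: "Date from which the analytical dataset is completely available".
- **Study length.** Section 9.1: "The study period is 30 months". Sections 4 and 7.2 also give 30 months. Section 6 lists a last interim report on 01 March 2024 and the final report on 30 September 2024.
- **Follow-up per person.** Section 9.1 runs it "until death, withdrawal of consent, loss to follow-up, 24 months or end of study period, whichever occurs first".
- **Target.** Section 9.2: "This primary data collection study will aim for up to 10,000 vaccine recipients with 2 years of follow-up data". To get there, 13,334 are to be enrolled, allowing 25% dropout over 2 years. Table 4 in Section 9.5 shows 10,000 as the expected number completing 24 months.
- **Late widening of entry.** Amendment 2, dated 07 January 2022, opens entry at second and booster doses. The amendment log in Section 5 says this was needed to reach the target size. The log lists no change to the milestones under that amendment.
- **Use made of 24 months.** Section 9.9 relies on the 24-month time frame to evaluate long-term safety.

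**The concern.** Two statements of how long the study runs cannot both be right, and the choice between them decides who can be followed for 24 months. On the Section 6 end date that group is limited to people indexed in the first two months. Entry was widened more than two months after that window closed. The step from 13,334 enrolled to 10,000 completers allows for dropout only and leaves no room for follow-up cut off by the calendar. At stake are the completer figure in Sections 4, 9.2 and 9.5, the premise of Table 4, and the long-term safety statement in Section 9.9 as it applies to second-dose and booster entrants.

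**Working it through.** **The plan's own figures first.** 10,000 / (1 − 0.25) = 13,334, as stated. The 25% block of Table 4 reproduces in all eight rows with exact Poisson limits on 13,334 × (0.75 × 2 + 0.25 × 1) = 23,334 person-years (PY). Every participant who does not drop out is therefore taken to contribute a full 24 months.

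**Calendar.** One month = 365.25/12 days.

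- "31 August 2021" to 31 October 2023 is 791 days = 26.0 months. Thirty months from the same start ends about 29 February 2024, so the gap is four months. The interim report of 01 March 2024 fits the 30 months.
- Last index date allowing 24 months: 31 October 2021 on the Section 6 end date, or about the end of February 2022 on 30 months.
- The inclusion criterion reads "Enrolment within 5 days of receipt of any dose", so enrolment itself could be as late as 5 November 2021.
- From 07 January 2022 to 31 October 2023 is 662 days, about 21.8 months. From the approval date, 18 January 2022, it is 651 days, or 21.4 months.
- Enrolling all 13,334 between 31 August and 31 October 2021 (62 days) means 13,334 / 62 ≈ 215 a day, about 11 a day at each of about 20 centres.

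**Scenarios.** The protocol gives no enrolment counts, so the calendars below are assumptions: 13,334 enrolled evenly over the interval, with 25% dropout spread evenly over 24 months. For a person with f = min(24, months from index date to end of collection):

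- expected PY = (f − 0.25 f²/48) / 12
- at f = 24 this is (24 − 3)/12 = 1.75, and 13,334 × 1.75 = 23,334, as behind Table 4
- completers = 13,334 × share able to reach 24 months × 0.75

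| Even enrolment | End of collection | Share able to reach 24 months | Completers | PY (vs 23,334) |
|---|---|---|---|---|
| 31 Aug 2021 to 28 Feb 2022 | 31 Oct 2023 | 62/182 days = 34% | about 3,400 | about 22,200 (−5%) |
| 31 Aug 2021 to 28 Feb 2022 | 29 Feb 2024 | 100% | 10,000 | 23,334 |
| 18 Jan to 18 Jul 2022 (extreme) | 31 Oct 2023 | 0% | 0 | about 18,480 (−21%) |
| 18 Jan to 18 Jul 2022 (extreme) | 29 Feb 2024 | 42/182 days = 23% | about 2,300 | about 21,830 (−6%) |

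**Precision.** At 10 events per 10,000 PY the exact 95% limits are 6.4 to 15.0 on 23,334 PY and 6.0 to 15.7 on 18,480 PY. The half-width goes from about 4.3 to about 4.9.

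**The case against.** The strongest reply is that one cell in the milestone table is out of line and the rest of the protocol says 30 months. Amendment 1 is logged as changing the start date and the report dates, without mention of the end date, so the cell may be a leftover. That is an inference, but a reasonable one. On 30 months the first scenario delivers exactly what the plan states. This part stands, so the point is first a contradiction between dates. A reader might infer that the 10,000 is out of reach on any reading; the documents do not support that.

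A second reply is that the target is worded as a maximum and that follow-up may end with the study, so no participant is promised 24 months. This is also true, and nobody should read the plan as breaking such a promise. But that wording does not repair the arithmetic. The inflation to 13,334 covers dropout alone, and Table 4 presents its 10,000 as completing 24 months.

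A third reply is that the primary estimate is a person-time rate, so truncated follow-up still counts, and that Table 4 already prints wider margins. This largely stands. At 10 per 10,000 PY the 40% block prints a margin of 6.0, wider than the 4.9 of the extreme scenario. Analyses confined to short windows after vaccination are hardly affected.

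Finally, a reader might take the zero completers and −21% as the expected loss. They require that nobody enrolled in the first four and a half months of data collection, which no section says. Amendment 2 shows that enrolment was short of target in January 2022, but not by how much.

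**Conclusion.** The contradiction is certain: 26.0 months in one place and 30 in the others. On the Section 6 end date, fewer than 13,334 can have been indexed in time for 24 months, because the target was still unmet on 07 January 2022. At the plan's own 25% dropout that gives fewer than 10,000 with 2 years of data. By how many fewer depends on enrolment counts that the protocol does not give; about 3,400 completers under even enrolment to the end of February 2022 is an illustration. On the same end date no second-dose or booster entrant admitted by Amendment 2 can be observed to month 24, so the long-term statement in Section 9.9 does not extend to them. Precision of the overall rates changes only modestly. Restoring 30 months resolves the matter fully only if the last index date is no later than about the end of February 2022, some six weeks after the amendment was approved.

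**What to change.** Reconcile Section 6 with Sections 9.1, 9.2, 9.5 and 9.9.

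1. At minimum, make the end of data collection agree with the 30-month study period, and state the last index date that allows 24 months (about the end of February 2022 on that period).
2. If enrolment will run later, or if 31 October 2023 is kept, replace the 10,000 with 2 years of data by the achievable number of completers and the range of follow-up. Base Table 4 on person-years from the actual enrolment calendar, and say in Section 9.9 that late entrants have no data to month 24.

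Restating the figures costs some text and one table, and the stated figures become less favourable. Moving the date costs some further months of questionnaires and may move the final report.

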7. RATIONALE AND BACKGROUND

7.1. Background

In December 2019, a novel coronavirus (severe acute respiratory syndrome coronavirus 2 [SARS-CoV-2]) was first identified by public health officials in China. The World Health Organization (WHO) declared the SARS-CoV-2 outbreak and associated disease (Coronavirus disease 2019 [COVID-19]) a global pandemic in March 2020 (1). Despite public health efforts, the incidence of COVID-19 has continued to rise, largely affecting middle-aged persons with worsening clinical sequelae linked to increasing age and comorbid conditions (e.g. cardiovascular disease, diabetes, and chronic lung disease) (2).

Given the rapid transmission of COVID-19 and incidence of disease in Europe, the rapid development of an effective vaccine is of utmost importance. Pfizer's and BioNTech's BNT162b2 vaccine candidate safety and efficacy are being tested worldwide in a diverse sample of subjects; however, individuals who are pregnant or immunocompromised are not included in the pivotal study, which has incorporated inclusion of subjects between 12 and 15 years of age (3). The Pfizer-BioNTech COVID-19 messenger ribonucleic acid (mRNA) vaccine has been granted conditional marketing authorization by the European Medicines Agency (EMA) for the prevention of SARS-CoV-2 infection. This study is part of a larger active surveillance plan to provide comprehensive information on real-world safety of the Pfizer-BioNTech COVID-19 mRNA vaccine within a 2-year period following vaccination of individuals within the European Union (EU).

7.2. Rationale

This prospective cohort study is designed as a 30-month non-interventional post-authorization safety study (PASS) including participants vaccinated with the Pfizer-BioNTech COVID-19 mRNA vaccine as an approved vaccine and followed for up to 24 months for the occurrence of selected safety outcomes. The medically attended safety events of interest in this study are based on the adverse events of special interest (AESI) defined by the Coalition for Epidemic Preparedness (CEPI)-funded Safety Platform for

Emergency vACCines (SPEAC) working with the Brighton Collaboration as well as the list of AESI from ACCESS. This group has identified a number of AESIs as a priority for PASS of COVID-19 vaccines. These AESIs include adverse events (AEs) previously identified with immunization in general (e.g. anaphylaxis, Guillain-Barré Syndrome [GBS]), with vaccine platforms (such as mRNA) relevant to COVID-19 vaccine development (such as vaccine-associated enhanced disease [VAED]), or with theoretical concerns based on immunopathogenesis (4, 5). Additional AESIs may be identified as information emerges about events potentially related to vaccines.

As vaccine recommendations are updated over time, approaches to investigating vaccine safety must flexibly account for this. Heterologous primary vaccination (two different COVID-19 vaccines [different manufacturers] received for the first and second doses of a primary [initial] course) and heterologous boosting (a third dose of a different manufacturers COVID-19 vaccine as a booster 3 to 6 months after a primary vaccination course) have joined vaccine recommendations. In light of this, this study will enroll participants based on receipt of the Pfizer-BioNTech COVID-19 mRNA vaccine, with Version 4.0 of the protocol amended to account for heterologous vaccination courses prior to or during the study period in order to reflect the real-world context of the study.

This non-interventional study (NIS) is designated as a PASS and is a commitment to the EMA.

8. RESEARCH QUESTION AND OBJECTIVES

The research questions addressed by this study are: a) What are the incidence rates of medically attended safety events of interest (based on the list of AESI) and other clinically significant events among persons vaccinated with the Pfizer-BioNTech COVID-19 mRNA vaccine, and b) Are these rates elevated relative to estimated expected rates?

Primary study objective:

- Estimate the real-world incidence of medically attended safety events of interest and other clinically significant events among individuals vaccinated with the Pfizer-BioNTech COVID-19 mRNA vaccine after authorization in the EU.

Secondary objectives:

- Evaluate whether the vaccine recipients experience increased risk of medically attended safety events of interest post-vaccination, via comparison with expected background rates and, as feasible, by self-controlled risk interval (SCRI) analysis;
- Estimate the incidence rates of medically attended safety events of interest among subcohorts of interest such as pregnant vaccine recipients, immunocompromised participants, and stratified by age.

9. RESEARCH METHODS

9.1. Study design

This is a prospective, observational, multi-center, non-interventional PASS conducted to evaluate safety of study participants receiving the Pfizer-BioNTech COVID-19 mRNA vaccine using a combination of primary data collection and secondary data analysis. This study will not provide or make recommendations on any vaccine use. Participants will be invited to enroll and consented in the study after the decision has been made to administer the vaccine, and participation in this study will not change or influence a participant's standard of care in any way. There are no protocol-mandated visits or procedures associated with the study. The study period is 30 months. Each participant will be followed from baseline (vaccination dose received at index date, where index date is defined as the date of Pfizer-BioNTech COVID-19 mRNA vaccine dose received within the 5 days prior to enrolment, regardless of dose number) until death, withdrawal of consent, loss to follow-up, 24 months or end of study period, whichever occurs first.

Data will be collected at baseline directly from the participants receiving the vaccine and/or their designee; this may include a health care provider (HCP) or study staff at the site administering the vaccine. Follow-up data on medically attended safety events of interest will be collected directly from persons receiving the vaccine.

[figure not shown]
This study will collect information on all reported occurrences of the medically attended safety events of interest, which is based on the AESI lists specified by ACCESSS and SPEAC/Brighton Collaboration, for which the participant sought medical care during the study period. Participants will choose their preferred method for submitting follow-up data:

- Completing questionnaires via a participant portal within the study website or mobile app, or
- Telephone interview via outbound calls from the IQVIA call center.

Data collection will be performed at baseline (Pfizer-BioNTech COVID-19 mRNA vaccine dose received at index date), and at weeks 1, 2, 4, 6, 8, 12 and every three months thereafter, through 24 months following index date (or until the occurrence of death, withdrawal of consent, loss to follow-up, or end of study period, whichever occurs first). In addition, data will be collected on any subsequent vaccine doses received during the study period. If a participant receives a subsequent Pfizer-BioNTech COVID-19 mRNA vaccine dose during the study period, the data collection schedule will reset based on the reported date of subsequent vaccine dose, with data collected at weeks 1, 2, 4, 6, 8, 12 and every three months thereafter from the reported date of subsequent vaccine dose only. If a participant receives another COVID-19 vaccine (**not** the Pfizer-BioNTech COVID-19 mRNA vaccine) dose during the study period, the data collection schedule will not reset, but the participant will remain in the study and the follow-up schedule will continue based on the previous Pfizer-BioNTech COVID-19 mRNA vaccine date. The observation period will not be extended if subsequent doses are received; the observation period will remain at 24 months following baseline (vaccination dose received at index date), or until the occurrence of death, withdrawal of consent, loss to follow-up, or end of study period, whichever occurs first.

An overview of the data collection schedule is shown in [Figure 1](#).

Figure 1. Data Collection Schedule

¹ Index Dose can be Dose 1, Dose 2 or Booster/Additional Dose

Participants may also report medically attended safety events of interest at any time outside of regular survey follow-up, via the participant portal within the study website or mobile app, or to the IQVIA call center.

Participant reported medically attended safety events of interest will be confirmed by the treating HCPs or through medical record documentation if needed to validate or establish the diagnosis associated with the event and validate the occurrence of a safety event of interest, or other clinically significant events. This process is further detailed in [Section 10](#).

